8.3.1.3 VISIT 2 (Day -14 \pm 3): Confirmation CAC

- *Update of Medical/Medication History*
- *Adverse Event Query*
- *Visual Acuity Utilizing an ETDRS Chart*: A clinically significant visual acuity decrease from Visit 1 may be documented as an AE per the investigator's discretion.

Confidential

Page 29

An increase of [REDACTED] or more should be brought to the attention of the investigator. Visual Acuity may be repeated in instances of significant decreases.

- Pre-CAC Ocular and Nasal Allergic Signs and Symptoms Assessments: The investigator and the subject will assess pre-CAC ocular and nasal allergic signs and symptoms using the Ora-CAC® scales. Subjects exhibiting a sign and/or symptom of allergic conjunctivitis [REDACTED] will be excluded.
- Slit Lamp Biomicroscopy
- Review of Inclusion/Exclusion Criteria
- Confirmation CAC: For each qualified subject, one drop of the allergen solution, of the same, final dose that elicited a positive reaction at Visit 1, will be administered bilaterally.
- Post-CAC Ocular and Nasal Allergic Signs and Symptoms Assessments: Assessments of itching will be made by the subject at 3(± 1), 5(± 1), and 7 (± 1) minutes following allergen challenge. Assessments of conjunctival redness and chemosis will be graded by the Investigator at 7(± 1), 15(± 1), and 20(± 1) minutes post-challenge and assessments of eyelid swelling, tearing/watery eyes, ocular mucous discharge, and nasal symptoms will be made by the subject at 7(± 1), 15(± 1), and 20(± 1) minutes post-challenge (Appendix 2). If the subject fails to react positively [REDACTED]
[REDACTED], he/she will be excluded from the study.
- Review of Inclusion/Exclusion Criteria
- Relief Drop Instillation: Subjects may receive a dose of a currently marketed, topical ophthalmic anti-allergic agent (i.e., anti-histamine/vasoconstrictor combination products like Visine®-A®) as they leave the office to relieve any immediate discomfort caused by the allergic reaction.
- Adverse Event Query
- Schedule Visit 3: Subjects will be asked to return to the office two (2) weeks later for Visit 3.

¹ not necessarily at the same time point

8.3.1.4 VISIT 3 (Day 1): Enrollment/Randomization/ In-Office Instillation/ Efficacy CAC/ Study Exit

- Update of Medical/Medication History
- Adverse Event Query
- Urine Pregnancy Test (for females of childbearing potential)
- Visual Acuity Utilizing an ETDRS Chart: A clinically significant visual acuity decrease from Visit 1 may be documented as an AE per the investigator's discretion. An increase of [REDACTED] or more should be brought to the attention of the investigator. Visual Acuity may be repeated in instances of significant decreases.
- Pre-CAC Ocular and Nasal Allergic Signs and Symptoms Assessments: The investigator and the subject will assess pre-CAC ocular and nasal allergic signs and symptoms using the Ora-CAC® scales. Subjects exhibiting a sign and/or symptom of allergic conjunctivitis [REDACTED] [REDACTED] will be excluded.
- Slit Lamp Biomicroscopy
- Review of Inclusion/Exclusion Criteria
- Randomization: Subjects who meet all of the inclusion criteria and none of the exclusion criteria and qualify to continue in the study will be enrolled and randomized to receive EM-100, Zaditor®, or the vehicle of EM-100. A separate treatment will be assigned to each eye. Subjects will be assigned the lowest four (4) digit randomization number available.
- Investigational Product Instillation: A trained study technician will instill one drop of the assigned treatment in the right eye and one drop of the assigned treatment in the left eye, according to the directions for use. The investigational product kit number and the time of instillation will be recorded. The pre-specified technicians responsible for instilling the investigational product will not be involved with any other study procedures at the site.
- Efficacy CAC: Each subject will receive one drop of the allergen solution of the same, final dose that elicited a positive reaction at Visit 1 bilaterally, 15(+1) minutes post-instillation of investigational product.
- Post-CAC Ocular and Nasal Allergic Signs and Symptoms Assessments: Assessments of itching will be made by the subject at 3(±1), 5(±1), and 7 (±1) minutes following allergen challenge. Assessments of redness and chemosis will be graded by the

Confidential

Page 31

Investigator at 7(± 1), 15(± 1), and 20(± 1) minutes post-challenge and assessments of eyelid swelling, tearing/watery eyes, ocular mucous discharge, and nasal symptoms will be made by the subject at 7(± 1), 15(± 1), and 20(± 1) minutes post-challenge (Appendix 2).

- Exit Slit Lamp Biomicroscopy
- Exit Visual Acuity Utilizing an ETDRS Chart: A clinically significant visual acuity decrease from Visit 1 may be documented as an AE per the investigator's discretion. An increase of [REDACTED] or more should be brought to the attention of the investigator. Visual Acuity may be repeated in instances of significant decreases.
- Relief Drop Instillation: Subjects may receive a dose of a currently marketed, topical ophthalmic anti-allergic agent (i.e., anti-histamine/vasoconstrictor combination products like Visine[®]-A[®]) as they leave the office to relieve any immediate discomfort caused by the allergic reaction.
- Adverse Event Query
- Study Exit: Subjects will be exited from the study.

Adverse Events (AEs) (both elicited and observed) will be monitored throughout the study. All AEs (both elicited and observed) will be promptly reviewed by the investigator for accuracy and completeness. All AEs will be documented on the appropriate eCRF.

If a female has a positive pregnancy test during the study, then the investigator will notify Ora immediately. The investigator shall request from the subject and/or the subject's physician copies of all related medical reports during the pregnancy and shall document the outcome of the pregnancy. The investigator will retain these reports together with the subject's source documents and will provide a copy of all documentation to Ora.

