7.1.2 Instructions for Use and Administration

- This trial requires additional attention in order to preserve masking of study treatment. There will be a total of 485 identical appearing kits containing all three treatments labeled A, B, and C. Once the kits arrive at the site, a designated staff member will randomly select 65 kits to be used for the trial. The remaining 420 kits will be identified and stored as retains. Both EM-100 and the vehicle of EM-100 will be identical in appearance as single use vials, while the reference product, Zaditor®, will be in its original bottle. All individual kits will be sealed with tamper evident tape and the sites will be instructed to not open the kits upon receipt of shipment. At no point during the trial (until database lock) will site staff or monitors be allowed to open the kits unless it is the designated “unmasked” technicians. These technicians will ensure that opening of the kits is done in a manner to prevent the other staff and subjects from seeing the investigational product. For each subject treatment will be administered by eye according to a randomization list which will be sent to the site in a sealed envelope and opened at Visit 3 by the unmasked technicians. Following Visit 3 dosing, the technicians will reseal the kits and randomization list envelope using tamper evident tape and return the kits to storage. The sealed randomization list envelope will be filed in the investigator’s study file.
- At Visit 3, qualifying subjects will be enrolled and randomized to receive EM-100, Zaditor®, or vehicle of EM-100. A randomization list will inform the technicians which corresponding letter treatment should be instilled in the right eye and which one should be instilled in the left eye.
- A trained study technician will instill one (1) drop of the assigned treatment in the right eye and one (1) drop of the assigned treatment in the left eye approximately 15(+1) minutes prior to CAC.

Confidential

Page 23

- The pre-specified unmasked technicians responsible for instilling the investigational product will not be involved with any other study procedures at the site. Care will be taken to hide the container (vial or bottle) from the subject. Dosing will occur in a room where no other subjects, staff, or investigators will observe the instillation.

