8.5 Compliance with Protocol

Subjects who are inappropriately enrolled or no longer fulfill the study eligibility criteria may be discontinued from the study. The reason for such discontinuation will be recorded as “protocol violation” in the source document and on the appropriate page in the eCRF.

Site staff will review concomitant medication by asking subjects if they changed their dosing regimen since their previous visit. The response will be recorded in the source document and on the eCRF at Visits 1, 2, and 3.

All protocol violations, regardless of causation, will be recorded in the subject’s source document as well as eCRF. Major protocol violations will be recorded in the subject’s source document, entered in the eCRF, and reported to the IRB, as per the applicable regulations.

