10.1.2 Per-Protocol Population

[REDACTED]

Confidential

Page 39

deviations. This population will be analyzed as treated using observed data only for confirmatory analyses. Major protocol deviations will be determined prior to unmasking any subject data.

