10.1.3 Safety Population

The safety population includes all subjects who received the test article. The safety population will be analyzed as treated and will be used for the safety analyses. No data will be excluded for any reason.

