10.9 Safety Analysis

Safety will be assessed by evaluating the incidence of subjects with any adverse events during the entire study. The percentage of subjects with any AEs will be summarized, as well as the percentage of subjects with any treatment-emergent adverse events (TEAEs), summarized for each treatment combination. Ocular TEAEs will similarly be summarized by eye for each treatment group. Incidence will be tabulated by MedDRA System Organ Class and preferred term within each system organ class. Adverse events will also be summarized for treatment-related TEAEs, SAEs, by maximal severity, and by day of onset relative to the start of treatment.

The additional safety variables of slit lamp biomicroscopy and visual acuity will be summarized descriptively using quantitative and qualitative summary statistics as appropriate. In all cases, outcomes will be summarized by eye for each treatment group. Changes and shifts from baseline will also be summarized where applicable.

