11.5.1 Labeling/Packaging

Each kit will contain the 3 treatments labeled A, B, and C. The EM-100 and vehicle will consist of five single use 0.4mL vials packaged in an aluminum pouch. Zaditor® will be in its original bottle with the label removed. A label containing the letter A, B, or C will be on the bottles of Zaditor® and the pouches of both EM-100 and vehicle of EM-100. There will be 485 kits created. Kits will be labeled on the outside with a kit number ranging from 001-485. Each kit will be sealed with tamper evident tape.

Confidential

Page 46

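### Do the as-treated analyses need a named record of which product each eye received?

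*Combined protocol and SAP*

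**What the plan says.** All references are to Amendment 2.0 unless stated otherwise.

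- **Analysis basis.** The visible part of Section 10.1.2 says of the per-protocol set: "This population will be analyzed as treated using observed data only for confirmatory analyses". It adds that major deviations are settled before any subject is unmasked. Section 10.1.3 says: "The safety population will be analyzed as treated and will be used for the safety analyses". Section 10.9 says: "Ocular TEAEs will similarly be summarized by eye for each treatment group".
- **Dosing.** Section 11.5.1: "Each kit will contain the 3 treatments labeled A, B, and C". Section 7.1.2: "A randomization list will inform the technicians which corresponding letter treatment should be instilled in the right eye", and likewise for the left eye. Section 8.3.1.4: "The investigational product kit number and the time of instillation will be recorded".
- **After dosing.** Used product goes back into the kit, which is resealed (Section 11.5.2). Section 7.1.2 says "At no point during the trial (until database lock) will site staff or monitors be allowed to open the kits", with an exception for the designated unmasked technicians. Section 11.5.3 tallies kits but does not count what is inside them. Section 11.5.4 allows return or destruction on site, to be specified in writing.
- **Errors and records.** Section 8.5: "All protocol violations, regardless of causation, will be recorded in the" source document and the eCRF. Section 11.4.1 lists a record of how the investigational product was distributed and used among the papers to be kept. Section 11.6 asks for complete and accurate recording of study data.

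**The concern.** An as-treated analysis needs to know what was given. The two dosing items named in Section 8.3.1.4 do not supply that. The kit number is the same whichever two of the three products were used, and the time says nothing about product. The letter for each eye comes from the randomization list, which states the assignment and not what was received. Dosing takes place out of sight of other staff, kits are resealed, and nobody counts their contents.

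Read this way, as treated differs from as randomized only where the technician noticed a mistake, so the per-protocol analysis would be a weak check on misdosing. By-eye adverse events rest on the same label. In a contralateral-eye design one swap misattributes data for two products at once. If EM-100 and Zaditor truly differ, swaps between them pull the estimated difference toward zero, which is the lenient direction for a non-inferiority claim.

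**Working it through.** **Inputs.** The original protocol's synopsis (Sample Size) gives 48 EM-100 eyes, 48 Zaditor eyes and 24 vehicle eyes. The split is blacked out in Amendment 2.0, but the total of 60 subjects is unchanged. The eye differences d = 0.5 and d = 1 on the itching scale are assumptions. No error rate is given and none is assumed.

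**The plan's own count.** (48 + 48 + 24)/2 = 60 subjects, which agrees. Let a, b and c be the EM-100/Zaditor, EM-100/vehicle and Zaditor/vehicle subjects. Then a + b = 48, a + c = 48 and b + c = 24, so a = 36, b = 12 and c = 12.

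**Is the kit number informative?** No. Three products in two eyes, different in each eye, give 3 × 2 = 6 ordered pairs, and all six are compatible with any kit.

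**When would a named source change the data?**

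1. *Assigned letters instilled.* As treated equals as randomized. Nothing changes.
2. *Error noticed.* Section 8.5 puts it in source and eCRF, and Section 10.1.2 settles major deviations before unmasking. The analyst corrects the product label or applies the deviation rule. Nothing is lost.
3. *Error not noticed.* It is in no record. A letter log would be filled in by the same technician reading the same list, so it may well show the assigned letter.

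Only the third case remains, and a look at opened pouches helps only partly. Two eyes and three letters give 9 ordered pairs, 8 of them wrong for a given subject. Using only the state of the EM-100 and vehicle pouches, and taking an opened pouch to mean that product was instilled, the errors that leave the expected state are:

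| Assigned pair | Not visible | Visible, at most |
|---|---|---|
| EM-100/Zaditor | eye swap; EM-100 in both eyes | 6 of 8 |
| EM-100/vehicle | eye swap | 7 of 8 |
| Zaditor/vehicle | eye swap; vehicle in both eyes | 6 of 8 |

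These are counts of error types, not frequencies, and they are upper bounds. Section 11.5.1 puts the letter on the pouch and mentions no vial label, and Section 7.1.2 says EM-100 and vehicle vials look identical. In an EM-100/vehicle subject both pouches are properly open, so vials mixed up afterwards would leave no trace. An eye swap is never visible.

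**Size of one unnoticed error.**

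- *Itching, one reversed EM-100/Zaditor pair.* The mean of 36 paired differences shifts by 2d/36, which is 0.028 at d = 0.5 and 0.056 at d = 1. If the analysis compares means over all 48 eyes per product, the shift is 2d/48, which is 0.021 and 0.042. The model is redacted, so both are shown.
- *Shrinkage.* With k reversed pairs of 36, the paired difference is multiplied by 1 − 2k/36: 0.944 for k = 1 and 0.833 for k = 3.
- *Vehicle pairs.* One reversed EM-100/vehicle pair multiplies the difference in eye means by 1 − 1/48 − 1/24 = 0.938. This works against the superiority test.
- *Safety.* One ocular event credited to the wrong eye shifts EM-100 minus Zaditor by 1/48 + 1/48 = 4.2 percentage points and EM-100 minus vehicle by 1/48 + 1/24 = 6.25 points. It requires a misdose and an ocular event in the same subject.

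**The case for a change.** The best case for a change is that a plan specifying as treated should name its source before unmasking. Two letter fields completed by staff who are already unmasked cost almost nothing, and once used kits are destroyed no physical check is possible. The use record in Section 11.4.1 has no stated eye-level content. The monitors' accountability review in Section 8.9 can reach no further than the kit tally of Section 11.5.3. Unnoticed swaps also favour non-inferiority, and the as-treated analysis could not correct them.

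The factual part stands: no visible text names an eye-level record of product received. It does not follow that none exists. The letter instilled would normally be entered on the dosing page, and no eCRF pages, dosing log, monitoring plan or separate SAP are in the file. The opening of the per-protocol definition is blacked out.

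The argument from unnoticed errors is weaker. A per-protocol set removes or relabels known departures; it is not a device for finding unknown ones. Neither a same-technician log nor a pouch check would catch most unnoticed eye swaps, the error that matters most here. The no-count rule also has a purpose: Zaditor is in a bottle and the other two products are in vials, so inspection by anyone else would threaten masking.

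**Conclusion.** No change to the plan follows. The missing sentence is a gap that analysts fill sensibly: the product received is the assigned letter, corrected by any dosing departure recorded before unmasking, using the technician's dosing record where it shows the letters. A check of kit contents would add little for the errors that matter and would sit awkwardly with masking.

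Per error, the effect is about 0.02 to 0.06 unit on the mean EM-100 minus Zaditor itching difference, and 4.2 or 6.3 percentage points on a by-eye safety contrast that is summarized without formal testing. These figures rest on the original protocol's eye counts, on assumed eye differences of 0.5 and 1 unit, and on a single error whose probability the documents do not give. If the assigned letters are instilled, every result is unaffected. Nothing is concluded about the primary analysis set, whose definition is redacted, and nothing in the documents suggests that misdosing occurred.

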8.3.1.2 VISIT 1 (Day -21 ± 3): Titration CAC

- Update of Medical/Medication History
- Adverse Event Query
- Urine Pregnancy Test (for females of childbearing potential): Females of childbearing potential must have a negative urine pregnancy test to continue in the study and must agree to use an adequate method of contraception for the duration of the study in order to be enrolled.
- Initial Visual Acuity Utilizing an ETDRS Chart: Subjects must have a score of [REDACTED] or better in each eye in order to qualify.
- Initial Ocular Itching and Conjunctival Redness Assessments: The investigator and the subject will assess initial ocular itching and conjunctival redness using the Ora-CAC® scales (see [Appendix 2](#)). Subjects exhibiting a sign and/or symptom of allergic conjunctivitis [REDACTED] will be excluded.
- Initial Slit Lamp Biomicroscopy: A slit lamp examination will be performed in both eyes to exclude subjects with disallowed ocular conditions (see [Appendix 2](#)). Findings of abnormality which are not exclusionary should be recorded as Medical History.
- Review of Inclusion/Exclusion Criteria: A review of protocol inclusion and exclusion criteria will be confirmed for each subject.
- Titration Conjunctival Allergen Challenge (CAC): A conjunctival allergen challenge (CAC) will be performed bilaterally with a perennial or seasonal allergen serially diluted in buffered saline and administered via a micropipette according to Ora SOPs. One drop of a solubilized allergen to which the subject is sensitized, at the weakest dilution, will be instilled bilaterally into the conjunctival cul-de-sac.

Confidential

Page 28

If the subject fails to react within 10 (± 2) minutes, increasingly concentrated doses may be instilled bilaterally at approximately ten-minute intervals until a positive reaction is elicited. If increasing doses are required (i.e., for insufficient bilateral itching and/or redness as evaluated by a trained technician or the Investigator), doses may be skipped. If a positive CAC reaction is not elicited with the first allergen [REDACTED] [REDACTED], other allergens to which the subject is sensitized may be used starting at the lowest dose.

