8.4.2 Unscheduled Visits

For unscheduled visits, the reason for the visit should be clearly documented on the appropriate eCRF, including findings from all evaluations that are completed.

Confidential

Page 32

These visits may be performed in order to ensure subject safety. All information gathered at unscheduled visits should be recorded on the Unscheduled Visit/Early Exit Visit pages of the source document and corresponding eCRF.

Evaluations that may be conducted at an Unscheduled Visit (as appropriate, depending on the reason for the visit), include:

- Assessment of Adverse Events
- Assessment of Concomitant Medications
- Visual Acuity Utilizing an ETDRS chart
- Urine Pregnancy Test (for females of childbearing potential)
- Slit lamp Biomicroscopy

If a randomized subject does not attend their scheduled visit, eCRF pages for missed visits will be skipped. All efforts should be made to schedule the subject for an Exit Visit to complete exit procedures.

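### The Visit 3 exit list puts the slit lamp before visual acuity, the reverse of every earlier visit, so the only post-dose acuity may not be measured under the same conditions as its baseline

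*Combined protocol and SAP*

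**What the plan says.** All references are to Amendment 2.0, the current protocol.

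- Section 8.3.1.2 (Visit 1) lists "Initial Visual Acuity Utilizing an ETDRS Chart", then the itching and redness assessments, then "Initial Slit Lamp Biomicroscopy".
- Section 8.3.1.3 (Visit 2) lists acuity, then the pre-challenge signs and symptoms, then "Slit Lamp Biomicroscopy".
- Section 8.3.1.4 (Visit 3) keeps that order before dosing, with "Visual Acuity Utilizing an ETDRS Chart" ahead of the slit lamp. After instillation, challenge and the gradings out to 20 minutes, the order reverses: "Exit Slit Lamp Biomicroscopy" comes first and "Exit Visual Acuity Utilizing an ETDRS Chart" is the next bullet.
- The exit acuity bullet takes Visit 1 as the reference. A clinically significant decrease may be recorded as an adverse event at the investigator's discretion, and the test may be repeated when the decrease is significant. No waiting time is given for the repeat.
- Section 10.9 treats acuity as a descriptive safety variable, summarized by eye for each treatment group, and adds: "Changes and shifts from baseline will also be summarized where applicable".

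**The concern.** A change from baseline is easiest to read when both measurements are taken under the same conditions. Here the listed conditions differ in one avoidable respect: the post-dose reading follows a slit lamp examination and the earlier readings do not. An examination with a bright beam immediately before a chart test could plausibly lower the score for a short time. That is general examination knowledge; the protocol does not state it.

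Acuity is one of three safety measures in section 6.2, and exit is its only scheduled post-dose reading. Subjects then leave the study, so no later scheduled reading could show that an apparent loss was transient. What is at stake is the absolute change from baseline in each treatment group and the investigator's comparison with Visit 1 when deciding whether to record an adverse event. The efficacy conclusions are not affected.

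**Working it through.** No sample size, power or error-rate figure is involved, so the check is a comparison of listed orders followed by reasoning.

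**Listed order, Amendment 2.0**

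| Occasion | Section | Listed first | Listed later |
|---|---|---|---|
| Visit 1 | 8.3.1.2 | Acuity | Slit lamp |
| Visit 2 | 8.3.1.3 | Acuity | Slit lamp |
| Visit 3, before dosing | 8.3.1.4 | Acuity | Slit lamp |
| Visit 3, exit | 8.3.1.4 | Slit lamp | Acuity |

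Acuity comes first at 3 of the 3 pre-dose measurements and second at the 1 post-dose measurement. The unscheduled-visit list in section 8.4.2 also names acuity first, but it is a menu ("Evaluations that may be conducted at an Unscheduled Visit (as appropriate, depending on the reason for the visit), include") and is not evidence of sequence. The original protocol and Amendment 1 have the same exit order, so neither amendment changed it.

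**Does list position mean time?** No visible sentence says so. The Visit 3 list nevertheless runs through eligibility review, randomization, instillation, challenge, gradings, exit examinations and study exit. The adverse event query appears near the start and again near the end, which makes sense only if position carries time. A site working down the list would do the slit lamp and then the chart.

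**Does the choice of baseline remove the mismatch?** No. The three candidate baselines are the Visit 1, Visit 2 and Visit 3 pre-dose readings, and all are listed before that occasion's slit lamp.

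**Would a shift differ between treatments?** It should not. Each subject receives different treatments in the two eyes, and both eyes go through the same exit list. A procedural shift should therefore fall about equally on EM-100, Zaditor and vehicle eyes. It would affect the level of change in each group, with no expected effect on the difference between groups.

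**How large could it be?** This cannot be computed. It would need the light effect on the chart score, the recovery time, the interval between the two examinations and the variability of repeat acuity. The visible text gives none of these, and the acuity alert threshold is redacted.

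**The case against.** The strongest reply is that this is only an observation about bullet order. Nothing visible makes the order binding, and the exit list does not look strictly sequential: section 8.2.2 allows relief drops only after all evaluations are complete, yet the list places them before the final adverse event query. The schedule in Appendix 1 and the examination procedures in Appendix 2 are not shown and may fix an order or a recovery interval. All of this stands, and it is why the point is conditional on the list being followed in order.

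Three stronger readings are tempting, and the documents support none of them.

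- A reader might infer that exit acuity is in fact taken after bright-light exposure and will show a false loss. The documents give neither the interval nor any effect of the slit lamp on acuity.
- A reader might want a count of eyes that would falsely cross an alert threshold. Every input to such a count would have to be assumed, and some eyes would cross from ordinary test-retest variation with no light effect at all.
- A reader might infer that a real loss in one eye would be hidden. The fellow eye has a different treatment and the same sequence, so it serves as a concurrent control.

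Two further replies limit the consequences. Adverse event recording requires a clinically significant decrease at the investigator's discretion, and a repeat test is permitted. This mitigation is partial, since the repeat is optional and has no set delay. Exit acuity also follows a bilateral allergen challenge, so it differs from baseline conditions whichever examination comes first. That difference is built into the design, whereas the examination order is an avoidable addition to it.

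**Conclusion.** The reversal is real and the protocol gives no reason for it. If the list is followed in order, post-dose acuity is measured just after a slit lamp examination and every possible baseline before one. The change-from-baseline summary and any judgement against Visit 1 may then carry a small procedural shift. Its size is unknown and may be nil.

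This rests on two assumptions: that sites work in listed order, and that some effect of the slit lamp persists when the chart is read. The first is likely from the structure of the lists but is not stated; the second is plausible but undocumented. Comparisons between treatments and the efficacy results are not expected to be affected. The point is minor and worth making because the correction is free.

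**What to change.** In section 8.3.1.4, list exit acuity before the exit slit lamp, after the 20-minute gradings, and align Appendix 1 if it shows the same order. All four scheduled acuity readings would then precede that occasion's slit lamp examination. The pre-dose slit lamp at Visit 3 would still come earlier the same day, but nominally at least 35 minutes before exit acuity (15 minutes from instillation to challenge plus 20 minutes to the last grading).

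If the present order is intended, the protocol should say so, state whether list order is binding, and point to any interval given in Appendix 2.

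The cost is swapping two bullets. No procedure, staff or visit time is added, and the allergen challenge remains a difference between baseline and exit that this change does not remove.
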